All patients will undergo a LGE-MRI within 30 days prior to the ablation procedure. The clinical purpose of the initial MRI is to define the anatomy of the heart chambers as well as the vessels for procedure planning. For research purposes, we will use this initial clinical MRI to delineate atrial structural remodeling or fibrosis to be used during the procedure in patients randomized to group 2 (pulmonary vein isolation + scar-based ablation) and for later analysis in all patients.

Imaging is done at our institution and will be reviewed for quality by the study staff. LGE-MRI sequences that do not meet quality standards for fibrosis analysis will not be further processed and these patients will be excluded from the study. Subjects for whom images are successfully evaluated will be randomized to the study groups.

This will be followed by block randomization in 1:1:1 format to a) pulmonary vein isolation (PVI) only (current standard of care), b) PVI plus targeting of dense LGE sites, which are confirmed on bipolar mapping to have voltage <0.1 mV, and c) PVI plus targeting of rotor anchor sites predicted by modeling.

At baseline, all patients will be evaluated for their quality of life (QOL) using the Short-form health survey (SF-36) (Ware & Sherbourne, 1992) for overall as well as AF-related impact on quality of life (Refer to additional study documents). The severity of symptoms will be tested using the European Heart Rhythm Association (EHRA) score of atrial fibrillation and the Canadian Cardiovascular Society (the CCS-SAF) scale (Dorian et al., 2006). Clinical data will be stored electronically and linked to a specific research ID number. Information linking de-identified data to the patients will be stored in the locked research office, in a password-protected file. Only members of the research team, in charge of collecting clinical information, will have access to this file. Individual subject binders containing signed consent forms and clinical source documentation will be labeled using study subject numbers and stored in the locked research office mentioned previously.

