A pre-ablation cardiac MRI is clinically indicated to assess baseline cardiac anatomy prior to procedure. Routine and LGE protocols will be used to acquire MR images. All patients will be asked to undergo a repeat LGE-MRI 12 months after the ablation. This is done for research purposes. Renal function is routinely monitored prior to gadolinium-enhanced MRI as a standard of clinical care.

With regards to the ablation procedure, all patients will undergo AF ablation. The procedure consists of circumferential pulmonary vein lesions under electro-anatomical guidance using CARTO (Biosense Webster Inc., Diamond Bar, CA). Operators will use either a 3.5mm irrigated tip radiofrequency ablation catheter (ThermoCool SmartTouch, Biosense Webster Inc., Diamond Bar, CA) or a cryoballoon catheter (Arctic Front Advance, Medtronic Inc., Minneapolis, MN). This procedure is FDA approved and will be conducted in all treatment arms according to standard of care. However, patients in the second group will undergo additional targeting of dense LGE sites, confirmed on bipolar mapping to have voltage <0.1 mV and patients in the third group will undergo targeting of rotor anchor sites as predicted by computational modeling. A detailed protocol of rotor ablation is described in the literature and shows no added complications compared to the conventional procedure (Narayan et al., 2014).

To prevent short-term recurrence of AF, patients will be kept on anti-arrhythmic regimen for the first 1 to 3 months after the ablation to be discontinued thereafter in the absence of AF recurrence, at the discretion of the treating physician. In addition, standard protocols for anticoagulation prior to, during, and after the ablation procedure will be applied.

After the ablation, clinical follow-up visits are scheduled at 3, 6 and 12 months. Research follow-up questionnaires and 12-lead ECG recordings will be done at the same day of the visits. All patients will undergo rhythm monitoring to detect AF recurrence using a portable, smartphone operated, AliveCor® Mobile ECG device. The AliveCor® Mobile ECG is a mobile, clinical-quality electrocardiogram (ECG) recorder. The software application can store thousands of recordings on smartphones or tablets and these recordings are wirelessly transmitted to AliveCor, Inc. (AliveCor) servers accessible to authorized users including healthcare providers. This device will be provided to the patients at no cost after enrollment in the study.

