During ablation, the spatial coordinates and electrogram characteristics of >200 intra-cardiac points are sequentially sampled and saved. We hypothesize that sites with slow conduction during sinus rhythm,

representing AF substrates, are detectable as sectors with intermediate LGE intensity [image intensity ratio (IIR) 0.9-1.6] on LGE-CMR. We will co-register the spatial coordinates of sites exhibiting slow conduction with pre-procedural LGE-CMR for 30 patients. We will then compare the baseline image intensity ratio of sites with slow conduction versus other sites.

Catheter ablation results in long-term AF suppression in approximately 50% of patients with persistent AF. We hypothesize that AF suppression at 1-year will be associated with the presence of IIR>1.6 at the 1-year LGE-CMR in sectors where slow conduction was observed at baseline. We will co-register the baseline spatial coordinates of sites exhibiting slow conduction with 1-year post-procedural LGE-CMR images for 30 patients randomized to ablation. We will then compare the 1-year image characteristics of sectors with slow conduction among patients with and without AF suppression at 1-year follow-up.

Catheter ablation promotes scar formation and more extensive ablation strategies may adversely affect left atrial function. However, AF recurrences and continuation of antiarrhythmic drug therapy may also lead to progression of atrial and ventricular dysfunction. We hypothesize that more extensive patient tailored approaches will have less negative impact on atrial and overall cardiac function. We will measure the change (baseline to 1-year MRI) in left atrial and left ventricular regional and global strain in 30 randomized patients. We will then examine the association of the change in regional and global strain with ablation strategy.

- c. Statistical plan including sample size justification and interim data analysis.

Based on the variable success rate of 40-80% in AF ablation, we anticipate that the study cohort of 30 patients would produce adequate sample size in all treatment arms and be sufficient to make meaningful statistical comparison.

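### Section 7b compares the IIR of slow-conduction sites with other sites: the size of a mean difference depends on where points were taken (in group 2 possibly guided by IIR), and it does not test the 0.9–1.6 band

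*Combined protocol and SAP*

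**What the plan says.** Section 7b of the combined protocol and SAP describes the data source: "During ablation, the spatial coordinates and electrogram characteristics of >200 intra-cardiac points are sequentially sampled and saved". Its hypothesis is that slow-conduction sites "are detectable as sectors with intermediate LGE intensity [image intensity ratio (IIR) 0.9-1.6] on LGE-CMR". The linkage step is "We will co-register the spatial coordinates of sites exhibiting slow conduction with pre-procedural LGE-CMR for 30 patients", followed by "We will then compare the baseline image intensity ratio of sites with slow conduction versus other sites". All three arms are therefore included. Co-registration is mentioned only for the slow sites.

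Section 4a says the baseline MRI will serve to "delineate atrial structural remodeling or fibrosis to be used during the procedure in patients randomized to group 2"; group 2 is the only arm named. It adds that "patients in the second group will undergo additional targeting of dense LGE sites, confirmed on bipolar mapping to have voltage <0.1 mV". Allocation is by "block randomization in 1:1:1 format", so group 2 is about 10 of 30 patients.

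Neither 7b nor the statistical plan in 7c gives a rule for point density, a weighting by area, a term for arm or patient in this comparison, or a statement of which saved points enter it. The documents do not say whether points taken to check a dense LGE target are among those saved.

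**The concern.** The points come from a treatment procedure, not from a mapping protocol fixed for research. In group 2 the operator has a reason to place points in dense LGE. If those points are saved and analysed, location has been selected on IIR, and IIR is then the outcome compared.

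Mean IIR of slow sites minus mean IIR of other sites depends on the mix of IIR values sampled. The hypothesis makes this worse: because it is a band, the other sites include tissue below 0.9 and tissue above 1.6. More points above 1.6 raise the mean of the other sites with no change in the tissue. Arms could show different associations from identical tissue, in data meant to support a later 300-patient trial.

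**Working it through.** The documents give no effect size, SD or frequency of slow sites for this objective, so there is no planned figure to reproduce. The check is an exact mixture calculation.

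**From the documents:** cut-points 0.9 and 1.6 (7b); at least 200 points per patient (7b), taken as 200; three equal arms (4a).

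**Assumed:** mean IIR *m* = 0.7, 1.2, 1.9 in the classes <0.9, 0.9–1.6, >1.6; share slow *p* = 5%, 30%, 5%, so the hypothesis is true; unsteered mix 60/30/10%, giving *n* = 120, 60, 20; 50, 100 or 200 extra dense-LGE points per group 2 patient; the other arms unsteered; sampling dependent on IIR only; points pooled unweighted.

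**Formula:** D = Σnpm/Σnp − Σn(1−p)m/Σn(1−p).

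**Unsteered.** Slow points 6, 18, 1: (4.2 + 21.6 + 1.9)/25 = 1.108. Other points 114, 42, 19: (79.8 + 50.4 + 36.1)/175 = 0.950. D = +0.158.

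**Group 2 with 100 extra dense points** (*n* = 120, 60, 120). Slow 6, 18, 6: 37.2/30 = 1.240. Other 114, 42, 114: 346.8/270 = 1.284. D = -0.044.

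**Pooled, one patient per arm** (*n* = 360, 180, 160). Slow 18, 54, 8: 92.6/80 = 1.158. Other 342, 126, 152: 679.4/620 = 1.096. D = +0.062, a loss of 1 − 0.062/0.158 = 61%.

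| Extra dense points per group 2 patient | Group 2 alone | Pooled |
|---|---|---|
| 0 | +0.158 | +0.158 |
| 50 | +0.027 | +0.104 |
| 100 | -0.044 | +0.062 |
| 200 | -0.110 | -0.001 |

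**Where the sign changes.** With the total held at 200 points, group 2 alone turns negative once about 32% of its points are dense; the pooled result turns only at about 77%. If points are added instead, the pooled result needs about 197 extra per group 2 patient. With an unsteered mix of 50/30/20%, the pooled result starts at +0.075 and turns at about 53% dense, or about 94 extra points.

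**Other tissue assumptions (60/30/10% mix, 0 to 200 extra points, pooled).** With 15% slow in dense LGE, D goes from 0.227 to 0.189. With 50% slow it goes from 0.419 to 0.540. The size moves and the sign does not. If the share slow never falls as IIR rises, sampling by IIR cannot reverse the sign.

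**A second set of assumptions.** Means 0.8, 1.2, 1.9; mix 50/40/10%; slow 10%, 30%, 5%. D starts at only +0.04. With 20%, 30% or 40% of group 2 points dense, group 2 gives -0.04, -0.10, -0.16 and the pooled result +0.02, -0.01, -0.04 (pooled mix = two unsteered arms plus group 2, divided by 3). With 10% slow in dense LGE, 30% dense moves group 2 from +0.07 to -0.03, with the pooled value still +0.04. With 20% slow, group 2 moves only from +0.12 to +0.10.

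**The band itself.** Take slow 5/30/5% and an unsteered mix of 40/30/30%: the band hypothesis holds strongly, yet D = -0.007. Take slow 5/30/50% and 60/30/10%: slow conduction is commonest above the band, so the hypothesis is false, yet D = +0.419. The mean difference does not separate the two. The share slow by class does (30% against 5%; 30% against 50%), and extra points within a class leave it unchanged while sampling depends on IIR alone.

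**The case against.** The strongest reply is that nothing in the documents establishes steering. Confirming a dense LGE site on bipolar mapping can mean reading voltage off the general map, with no added points. That is a fair reading; the point is conditional on the checking points being saved and used, and the extra-point counts above are assumptions.

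A second reply is that section 7b says only that IIR will be compared, not that means will be. If the outcome is instead whether IIR falls in the band, the second set of assumptions gives 69% of slow against 34% of other sites in the band when unsteered (odds ratio 4.2). With 40% dense points in group 2 it gives 60% against 22% in that arm (5.5) and 66% against 30% pooled (4.6). The direction cannot reverse while in-band tissue is the most often slow. This stands, and it supports an analysis by class.

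A reader might infer that the sign of the 30-patient result hangs on operators' habits. The documents do not support that. A pooled reversal needs slow conduction to be rare in dense LGE together with heavy steering or a starting difference near zero. A reader might also take PVI-only mapping to be unsteered. Every patient has a planning MRI and no blinding of operators to LGE is described, so that cannot be assumed either.

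Finally, invariance of the class shares is a property of the assumption, not a finding. It fails if points are chosen on voltage as well as IIR.

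**Conclusion.** The concern holds in conditional form. If target-confirmation points enter the comparison, the size of a mean IIR difference depends on point density and can differ by arm. On the main assumptions, 100 extra dense points per group 2 patient remove about 61% of the pooled difference. The sign can reverse within group 2 when slow conduction is rare in dense LGE; pooled reversal is confined to the narrow conditions above. Inclusion of the checking points and unweighted pooling are inferences from a plan that is silent on both.

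The second part does not depend on steering: with sites on both sides of the band counted as other, a mean difference does not test the stated 0.9–1.6 hypothesis.

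This concerns a secondary objective of a preliminary study and does not touch the primary outcome. It is a cheap improvement.

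**What to change.** In section 7b:

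1. Make the main analysis the within-patient share of points with slow conduction by IIR class (<0.9, 0.9–1.6, >1.6), with patient as cluster. State that all saved points are co-registered, not only the slow ones.
2. Flag, at the procedure, points added to confirm an LGE or rotor target, and leave them out of this analysis. The class shares are protected only when sampling depends on IIR alone, and points taken to check low voltage may not meet that condition.
3. Show the result by arm as a sensitivity check, without describing PVI-only mapping as unsteered.

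The cost is a flag recorded during the procedure, a few sentences in 7b, co-registration of the remaining points if not already intended, and somewhat fewer points in groups 2 and 3. A description of mean IIR at slow and other sites can be kept alongside, since section 2 asks for the image characteristics of slow-conduction substrate.

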Comparison variables will be presented as means \pm SD, and categorical variables as numbers and percentages. Differences between treatment groups will be assessed using the Pearson Chi-square test and the Wilcoxon rank-sum test. Survival curves for time to event analysis will be estimated using the Kaplan-Meier method, and the differences between the curves will be tested for significance with the log-rank statistic. Weekly event rates will be calculated by dividing the event rate by the maximum follow-up period in each arm of the Kaplan-Meier analysis. Hazard ratios will be calculated by univariate and multivariate analysis using the Cox proportional-hazards regression model. When comparing MR image characteristics as well as LA function between pre and post-ablation imaging, the Student's t-test will be using for comparison of the means. All statistical testing will be 2-tailed. Results will be considered statistically significant at a level of $p < 0.05$.

- d. Early stopping rules. N/A

8. Risks

- a. Medical risks, listing all procedures, their major and minor risks and expected frequency.

As discussed above, all procedures except the post-ablation MRI is part of the standard clinical care. In addition, groups reporting their experience with substrate-based ablation have not encountered increased complications compared to the conventional ablation procedure (Narayan et al., 2012). In addition, there is no data suggesting any health hazard associated with magnetic field exposure (Schenck, 2000). All patients with pacemakers, implanted defibrillators or electronic/metallic devices, shrapnel and other metals such as metal in the eyes will be excluded.

Gadolinium chelates used as intravenous contrast media in MRI are considered safe and do not exhibit the nephrotoxicity associated with iodinated media. The injection of contrast intravenously is not painful, but

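### Sections 7b and 7c set no unit of analysis for the site and sector MRI comparisons; if sectors are pooled, the AF-suppression comparison exceeds its nominal 5% error rate

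*Combined protocol and SAP*

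**What the plan says.** Section 7b (Secondary outcome variables) describes mapping during ablation in which the "electrogram characteristics of >200 intra-cardiac points are sequentially sampled and saved". Two comparisons use the mapped sites after co-registration with MRI.

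- Baseline: "We will then compare the baseline image intensity ratio of sites with slow conduction versus other sites".
- One year: the hypothesis reads: "AF suppression at 1-year will be associated with the presence of IIR>1.6 at the 1-year LGE-CMR in sectors where slow conduction was observed", where slow conduction is taken from the ablation mapping. The planned comparison is: "We will then compare the 1-year image characteristics of sectors with slow conduction among patients with and without AF suppression at 1-year follow-up".

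Both analyses are stated to cover 30 patients. A third secondary outcome concerns strain: "We will then examine the association of the change in regional and global strain with ablation strategy".

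Section 7c (Statistical plan) gives these methods for comparing values or proportions:

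- "Differences between treatment groups will be assessed using the Pearson Chi-square test and the Wilcoxon rank-sum test".
- Student's t-test, with this scope: "When comparing MR image characteristics as well as LA function between pre and post-ablation imaging".

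It adds "All statistical testing will be 2-tailed" and sets significance at p < 0.05. Its remaining methods (Kaplan-Meier, log-rank, Cox) are for time to event. It names no test for slow versus other sites or for suppressed versus non-suppressed patients. It mentions no per-patient summary, mixed model, GEE or clustered variance, and no other section supplies one.

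**The concern.** Sites and sectors from one atrium, imaged on one scan, are likely to resemble each other more than sectors from different patients. Chi-square, rank-sum and ordinary t-tests treat every observation as separate evidence. Whether a patient had AF suppression is known once per patient, so ten sectors from that patient are not ten independent pieces of evidence about suppression.

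Two of the three secondary objectives in section 2 rest on these comparisons: the image characteristics of slow-conduction substrate, and the structural changes associated with suppression. The study is also meant to supply preliminary data for a 300-patient trial (section 1), so a spurious sector-level association could influence that design. With only 30 patients, a sector-level analysis is tempting because it makes the sample look much larger. If the unit is left open, it can be chosen after the data are seen.

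**Working it through.** **Inputs from the documents.** Two-sided alpha 0.05 (7c). 30 patients (7b). Long-term suppression in about 50% (7b), hence about 15 versus 15.

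**Assumed inputs.** The documents give neither the number of slow-conduction sectors per patient (m) nor the ICC. I use m = 5 and 10, and ICC = 0.01, 0.1 and 0.3.

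**1. AF-suppression comparison, sectors pooled.** With m sectors from each of 15 patients per group and total variance σ², the true variance of a group mean is σ²/(15m) × [1 + (m − 1) × ICC]. A test that assumes independence uses about σ²/(15m). With DE = 1 + (m − 1) × ICC, the actual two-sided error is

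2 × [1 − Φ(1.96/√DE)].

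Check against the plan's own figure: m = 1 or ICC = 0 gives DE = 1 and an error of 5.0%, which is the stated alpha.

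| m | ICC | DE | 1.96/√DE | Actual error |
|---|---|---|---|---|
| 5 | 0.01 | 1.04 | 1.922 | 5.5% |
| 5 | 0.1 | 1.40 | 1.657 | 9.8% |
| 10 | 0.1 | 1.90 | 1.422 | 15.5% |
| 10 | 0.3 | 3.70 | 1.019 | 30.8% |

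Simulated pooled t-tests (15 versus 15, normal data, 5,000 runs per setting) gave 5.6%, 9.8%, 15.2% and 30.4% for the four rows. A pooled rank-sum test gave 5.5%, 10.2%, 15.1% and 29.7%.

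**2. Same comparison, one value per patient.** In the same four settings, a Wilcoxon test on each patient's share of sectors above a cut (30% of sectors positive, assumed) gave 4.1% to 4.9%. A t-test on patient means gave 4.3% to 5.5% over m = 5, 10, 20 and ICC 0 to 0.3 (4,000 runs per setting).

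**3. Slow versus other sites.** This is a within-patient contrast, so the result differs. Assume 30 patients with 40 slow and 160 other sites each, and ICC 0.3.

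- *Only the patient's overall level varies.* That level cancels from the slow-minus-other difference, but a pooled test still counts it as noise. The true variance is about 0.7 of the variance used, so the error is 2 × [1 − Φ(1.96/√0.7)] = 1.9% (simulated 1.6%), which is below 5%.
- *The slow-minus-other difference also varies between patients, with variance 0.05.* The true variance is 0.05/30 + 0.7 × (1/1200 + 1/4800) = 0.00240. The pooled test uses about 1.01 × (1/1200 + 1/4800) = 0.00105. The ratio is 2.28, giving 19% (simulated 20%).
- *The same with variance 0.2.* The ratio is 6.83, giving 45% (simulated 44%).

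A paired test on one difference per patient gave 4.4% to 5.3% in all three cases.

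**The case against.** The best defence is that the plan never says sectors will be pooled. Section 7b counts both analyses in patients and groups the 1-year comparison by patients with and without suppression, and the sample-size statement in 7c counts patients too. A competent analyst could take the patient as the unit and no harm would follow. The objectives concerned are secondary, in a small study gathering preliminary data.

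Much of this stands. It makes the harm conditional and limits its weight. It does not settle the unit: 7b also speaks of sites versus other sites and of characteristics of sectors, and 7c offers only independent-observation tests for comparisons of this kind.

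A reader might infer more than the documents support:

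- **That the plan pools sectors.** It leaves the choice open.
- **That more than 200 is the cluster size, so the error is extreme.** That number counts all mapped points, not slow-conduction sectors.
- **That confidence intervals will be too narrow.** Section 7c plans none for these comparisons.
- **That the regional strain analysis is inflated.** Section 7b does not say that several regions per patient will be analysed together, so no size can be given.
- **That the trial's main result is at risk.** Time to recurrence has one observation per patient.

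**Conclusion.** The omission is certain from the text: there is no unit of analysis, no named test and no allowance for within-patient correlation in either comparison. The consequence is conditional. If the listed tests are applied to sectors, the suppression comparison exceeds 5% for any positive ICC with two or more sectors per patient. The excess runs from negligible (5.5%) to severe (31%) over the assumed values shown, and the documents do not allow it to be narrowed. A positive ICC is an assumption, though a mild one for sectors of the same atrium. For slow versus other sites, the direction of the error is not determined in advance. This should be fixed before these data are analysed, as a short clarification of secondary analyses.

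**What to change.** Add to section 7c:

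> The patient is the independent unit for all site and sector comparisons. Slow versus other sites: one slow-minus-other difference in mean IIR per patient, tested with a paired t-test. One-year suppression comparison: one summary per patient (for example, the share of slow-conduction sectors with IIR >1.6), compared by Wilcoxon rank-sum. A mixed model or GEE with patient as the cluster and a small-sample correction is an acceptable alternative. The number of contributing patients is reported as the sample size. If several regional strain values per patient are analysed together, the same rule applies.

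The investigators should confirm the share as their reading of the 7b hypothesis. Its wording could also mean any sector above 1.6, or each sector separately, and the choice defines the endpoint.

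The change needs plan wording and standard software only. Its cost is lower apparent precision, which reflects what 30 patients can show:

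- **Suppression comparison, 15 versus 15, 80% power.** The normal approximation gives (1.96 + 0.84) × √(2/15) = 1.02 between-patient SD. With the t distribution it is 1.06, and by Wilcoxon about 1.1.
- **Paired comparison, 30 patients, 80% power.** The approximation gives 2.80/√30 = 0.51 SD of the per-patient differences. With the t distribution it is 0.53.

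Both thresholds rise if fewer than 30 patients contribute, for example because a 1-year MRI is missing.

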The main objective of the study is to identify the optimal ablation strategy for suppression of persistent AF.

The secondary objectives of the study are:

- To define the local myocardial image characteristics of slow conduction AF substrates.
- To define the local myocardial structural changes post ablation that associate with AF suppression at 1-year follow-up
- To compare cardiac remodeling and atrial function at 1-year follow-up between PVI only and tailored catheter ablation groups

3. Background

Atrial fibrillation (AF) is associated with increased risk for mortality, heart failure, and thromboembolic events, and has a worldwide prevalence of >33.5 million (Benjamin et al., 1998; Chugh et al., 2014; Estes et al., 2011; Schnabel et al., 2015). Catheter ablation of AF is evolving as an effective therapy for symptomatic AF (Calkins et al., 2012). Recurrent AF after ablation, however, remains a problem and has been reported to associate with the baseline extent of left atrial (LA) late gadolinium enhancement (LGE) on cardiac magnetic resonance (CMR) (Marrouche et al., 2014; McGann et al., 2014). Mechanistically, persistent AF appears to be more reliant upon fibroblast proliferation and myocyte-fibroblast coupling than paroxysmal AF, which is primarily dependent upon pulmonary vein triggers (Haissaguerre et al., 1998; Inoue et al., 2012; Wilber, 2012). Therefore, we hypothesize that the substrate for persistent AF is detectable on atrial LGE-CMR and variable among patients, and that the substrate predicts patient outcomes after anatomic non-tailored ablation, and is more likely to respond to individually tailored ablation approaches. Two individually tailored approaches will be studied including empiric targeting of dense LGE, confirmed on bipolar mapping to have voltage <0.1 mV, and modeling based targeting of rotor anchor sites.

4. Study Procedures

a. Study Design

Initially, we propose prospective enrollment of 30 participants with persistent AF. Patients presenting to our institution who meet the inclusion criteria will be asked to participate in the study. All patients will undergo routine clinical care including echocardiography as indicated.

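### The structural-change objective is tested on the 1-year image alone, so scar already present before ablation counts as ablation effect and can dilute the association with AF suppression

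*Combined protocol and SAP*

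**What the plan says.** Section 2 (Objectives) gives as the second of three secondary objectives (objective 2 here): "To define the local myocardial structural changes post ablation that associate with AF suppression at 1-year follow-up".

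Section 7b (Secondary outcome variables) turns this into a hypothesis that AF suppression at 1 year will be "associated with the presence of IIR>1.6 at the 1-year LGE-CMR in sectors where slow conduction was observed at baseline". The data step is: "We will co-register the baseline spatial coordinates of sites exhibiting slow conduction with 1-year post-procedural LGE-CMR images for 30 patients randomized to ablation". The analysis step is: "We will then compare the 1-year image characteristics of sectors with slow conduction among patients with and without AF suppression at 1-year follow-up".

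Three other places bear on the point:

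- For the first secondary objective, Section 7b hypothesises that slow-conduction sites "are detectable as sectors with intermediate LGE intensity [image intensity ratio (IIR) 0.9-1.6] on LGE-CMR", and plans: "We will co-register the spatial coordinates of sites exhibiting slow conduction with pre-procedural LGE-CMR for 30 patients". The baseline image value of these sites will therefore be available.
- For the third secondary objective, Section 7b uses change in strain from the baseline MRI to the 1-year MRI.
- Section 3 (Background) states that recurrent AF after ablation "has been reported to associate with the baseline extent of left atrial (LA) late gadolinium enhancement (LGE") on cardiac MR.

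Section 7c names a t-test for image characteristics before versus after ablation. It does not relate that change to AF suppression.

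**The concern.** The objective is about change, but the variable is an end state. Sectors enter because conduction was slow at baseline, not because of their baseline IIR. Nothing in Section 7b subtracts the baseline IIR, adjusts for it, or sets aside sectors that were above 1.6 before any lesion was made. IIR>1.6 at 1 year therefore mixes two things: scar made by ablation, which the hypothesis links to suppression, and scar that was there already.

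The two may pull in opposite directions. If more baseline enhancement goes with recurrence, as Section 3 reports for the left atrium as a whole, old scar adds to the 1-year figure mainly in recurrent patients, while the hypothesis expects the higher figure in suppressed patients. At stake is whether a real link between new scar and suppression is understated or missed in preliminary data that are meant to precede a 300-patient trial.

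**Working it through.** **Plan's own figure.** There is none to reproduce. The documents give no effect size, power or baseline share of IIR>1.6 for this objective.

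**Inputs from the documents.** Cut-off 1.6, hypothesised baseline range 0.9-1.6, 30 patients, and about 50% long-term suppression (all Section 7b). That makes about 0.5 × 30 = 15 suppressed and 15 recurrent patients.

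**Assumed inputs.** b = share of slow-conduction sectors already above 1.6 before ablation. c = share of the remaining sectors that ablation converts to above 1.6. A sector above 1.6 at baseline is taken to stay there.

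**Formula.** Share above 1.6 at 1 year: Y = b + (1 - b)c.

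With true conversion of 35% (suppressed) v 20% (recurrent), a 15-point difference:

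| Baseline b, suppressed v recurrent | Y suppressed | Y recurrent | Difference seen |
|---|---|---|---|
| 0% v 0% | 0.350 | 0.200 | 15 points |
| 10% v 10% | 0.10 + 0.90×0.35 = 0.415 | 0.10 + 0.90×0.20 = 0.280 | 13.5 |
| 2% v 5% | 0.02 + 0.98×0.35 = 0.363 | 0.05 + 0.95×0.20 = 0.240 | 12.3 |
| 5% v 15% | 0.05 + 0.95×0.35 = 0.3825 | 0.15 + 0.85×0.20 = 0.320 | 6.3 |
| 10% v 25% | 0.415 | 0.25 + 0.75×0.20 = 0.400 | 1.5 |
| 10% v 30% | 0.415 | 0.30 + 0.70×0.20 = 0.440 | -2.5 |

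Cancellation point with 10% in suppressed patients: 0.20 + 0.80b = 0.415 gives b = 0.215/0.80, about 27% in recurrent patients.

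The error can also create a difference. With 25% conversion in both groups and b = 10% v 25%, Y is 0.325 v 0.4375, about -11 points where the truth is zero.

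**Second check, by simulation** (400,000 patients per scenario, all inputs assumed). Conversion has mean 0.40 and SD 0.15. The log-odds of suppression rise by 1.0 per SD of conversion and fall by k per SD of baseline scar. Entries are the suppressed-minus-recurrent difference in the 1-year share.

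| Mean (SD) baseline scar | k = 0 | k = 0.5 | k = 1.0 | k = 1.5 |
|---|---|---|---|---|
| 0.10 (0.10) | +0.114 | +0.087 | +0.062 | +0.040 |
| 0.20 (0.15) | +0.101 | +0.063 | +0.025 | -0.006 |
| 0.30 (0.20) | +0.088 | +0.038 | -0.010 | -0.049 |
| 0.40 (0.25) | +0.076 | +0.013 | -0.046 | -0.095 |
| Difference in conversion itself | about +0.126 | about +0.12 | about +0.11 | about +0.10 |

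With no baseline scar the two measures coincide (+0.126 at k = 0). When baseline scar is unrelated to outcome (k = 0) there is dilution only. A change of sign needs roughly 20-30% or more of sectors above 1.6 before ablation and a baseline-scar effect at least as strong as the ablation effect. At 15 v 15, two-sided 0.05, normal approximation, the scenario with mean 0.20 and k = 1.0 has power of about 7% on the 1-year share and about 58% on conversion.

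**The case against.** **The plan is coherent under its own hypothesis.** If slow-conduction sectors all start at 0.9-1.6, a value above 1.6 at 1 year is new scar and nothing is wrong. This stands as the main limit. But that range is the claim the first secondary objective sets out to test, not a rule for selecting sectors. The same analysis would reveal a departure, yet Section 7b does not say what would then happen to the objective 2 comparison.

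**Section 3 speaks of the extent of left atrial LGE,** not of IIR>1.6 in slow-conduction sectors. This also stands: applying its direction to these sectors is an inference. Without it, baseline scar still dilutes (13.5 of 15 points at 10% v 10%).

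**The objective could mean findings after ablation rather than change.** The hypothesis is indeed worded as an end state, so this is partly fair. But an end state cannot be attributed to ablation without the baseline, and the strain objective in the same section uses change.

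**Section 7c covers it.** It does not. The pre/post t-test is not split by AF suppression, and the multivariate Cox model names no covariates and is not assigned to this comparison.

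A reader might infer two stronger things. One is that the arm targeting dense LGE makes the problem worse. The documents do not support this: patients are randomised after imaging, targeting scar does not create baseline scar, dense LGE is given no IIR cut-off, and nothing says the dense low-voltage targets are the slow-conduction sectors. The other is that the comparison will come out null or reversed. That needs common, strongly prognostic baseline scar in these sectors, for which the documents give no figure.

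**Conclusion.** The concern holds in a limited form. The mismatch is plain from the text: an objective about change is tested on a 1-year value with no baseline image term. Its consequence is conditional. The error is zero if no slow-conduction sector exceeds 1.6 before ablation, and small if few do or if baseline scar is modest and similar in both outcome groups. It becomes serious only as baseline scar grows common and differs by outcome. The full illustrated range, from 15 points down to -2.5 for a true 15, rests on assumed shares, so it shows what is possible rather than what to expect. This is a secondary, mechanistic objective in a 30-patient study, and the primary comparison of ablation strategies is unaffected. It should still be corrected, because the correction uses data the plan already collects.

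**What to change.** In Section 7b, replace the objective 2 analysis sentence with one that uses the pre-ablation IIR of the same co-registered sectors:

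- **Main analysis:** compare IIR>1.6 at 1 year between suppressed and recurrent patients, adjusted for baseline IIR of the sector, with sectors clustered within patient.
- **Alongside it:** report, per patient, the share of slow-conduction sectors with IIR≤1.6 before ablation that exceed 1.6 at 1 year.
- **Descriptive only:** the unadjusted 1-year comparison.

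The adjusted comparison should lead because it keeps every sector. The new-scar summary drops those already above 1.6, which removes most from patients with the most baseline scar, and it counts a small drift across the cut-off as new scar.

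The cost is a sentence or two of protocol text and slightly more analysis. Both MRIs are already scheduled for all patients, and the slow-conduction sites are already to be registered to both. If all sectors do start at or below 1.6, the new-scar summary equals the planned 1-year share and nothing is lost.
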